2.2 Study Device Information

Miltenvi Biotec. Inc.

Brand: CliniMACS® CD34 Reagent System Information

The CliniMACS® CD34 Reagent System is a medical device that is used in vitro to select and enrich specific cell populations.

The CliniMACS® CD34 Reagent System is comprised of four primary components:

- CliniMACS® CD34 Reagent: a sterile monoclonal antibody reagent specific for CD34+ cells.
- CliniMACS® plus Instrument: a software controlled instrument that processes the blood sample (cell product).
- CliniMACS® Tubing Sets: single-use, sterile, disposable tubing sets with two proprietary cell selection columns (CliniMACS® Tubing Set and CliniMACS® Tubing Set LS)
- CliniMACS® PBS/EDTA Buffer: a sterile, isotonic phosphate-buffered, 1 mM EDTA, saline solution, used as external wash and transport fluid for the in vitro preparation of blood cells

Distributor:

Corporate Headquarters Miltenyi Biotec Inc. [name]

Manufacturer:

Miltenyi Biotec GmbH, Clinical Products [name]
Bergisch Gladbach, Germany

Manufacturer Contact: Miltenyi Biotec Inc., [name]

[name] [contact] [contact]

CliniMACS $^{\circ}$ Tubing Sets (Standard and Large Scale) Standard: Up to 0.6 x 10 $^{\circ}$ CD34+ cells from up to 60 x 10 $^{\circ}$ Cells

Large Scale: 0.6-1.2 x 109 CD34+ cells from 60-120 x 109 Cells

CliniMACS® CD34 Reagent

CliniMACS® PBS/EDTA Buffer

2.3 Rationale

Cell dose is the most important factor affecting clinical outcomes in adult patients undergoing transplantation. Transplantation with a cell dose of less than 2.5×10^7 nucleated cells per kilogram or a CD34 dose of less than 1.7×10^5 per kilogram is associated with higher rates of non-engraftment, non-relapse mortality and lower survival (14). Alternative donors can provide ideal cell dose grafts and have the advantage of being rapidly available, but the higher probabilities of severe acute and extensive chronic GvHD due to HLA-mismatched is a significant source of morbidity and mortality. This study provides access to a model that potentially benefits from alternative NMDP and related donor pools to test the safety and efficacy of manipulated grafts using the CliniMACS® System. The aim is to ensure robust cell dose grafts with the best available donor for allogeneic HSCT recipients while providing a method for T cell depletion through CD34+ selection as the single form of GvHD prophylaxis. Currently, there is not a FDA-approved method for this process in the United States.

The outcomes in relatively small studies for children receiving unrelated donor transplants using the CliniMACS® have been comparable to or better than those receiving T cell depleted transplants with post-transplant immunosuppression (21, 25). This study will enroll up to 30 transplant recipients at Stanford. As the recommended prescription of allogeneic transplantation for different underlying diseases grows, enrollment on this protocol is expected to gradually increase in relation to the overall number of transplants performed in our center.

2.4 Study Design

This is a PI-initiated, single institution, open (no masking is used), prospective study to provide access to allogeneic graft manipulation through CliniMACS® System for qualifying candidates.

Currently, no FDA-approved method for T cell depletion exists. Recent experience with the CliniMACS® device has produced results with a 70-75% survival in children, many of whom were high-risk patients (19, 22, 36).

Patients will be enrolled with alternative (mismatched/haplocompatible) donors for an initial transplant.

The results with mismatched related or unrelated donor transplants so far justify expanding this approach to related donor recipients who have contraindications to post-transplant immunosuppression due to borderline organ function. Matched-related or unrelated donor recipients with borderline organ function will be allowed to enroll.

It is anticipated that the use of the CliniMACS® device will result in a very low risk of GvHD without the need for post-transplant immunosuppression.

This protocol will allow the use of patient-specific conditioning regimens that are available through open IRB studies in our institution or through open treatment plans from either the pediatric or adult stem cell transplant groups at Stanford University.

The follow-up schedule and affiliated data collection forms for the allogeneic recipients in this study are the standard CIBMTR data forms and procedures.

All recipients enrolled in the study and will be assessed for: neutrophil and platelet engraftment, graft rejection, serious infusion reaction, transmission of infection from HSCs infusion, EFS, TRM, acute and chronic GvHD, HSCT-related toxicities.

3. PARTICIPANT SELECTION AND ENROLLMENT PROCEDURES

Refer to the Participant Eligibility Checklist in Appendix A.

3.1 Inclusion Criteria

- · Participants greater than one month of age.
- Participant has a disorder that can be treated with a hematopoietic stem cell transplant
- Participant's is eligible for an allogenic HSCT as per current institutional SOP and FACT standards.
- Participant must have a related or unrelated matched or mismatched-related donor who is:
- Able to receive granulocyte colony-stimulating factor (G-CSF) and undergo apheresis either through
 placement of catheters in antecubital veins or a temporary central venous catheter OR agrees on a bone
 marrow harvest;
- Healthy as per donor selection screening (following current SOP based on standards of foundation for accreditation of cellular therapy and stem cell transplantation – FACT);
- · Willing to participate and sign consent.
- Participant or Legal Authorized Representative is able to signinformed consent (and signed assent, if applicable) for transplant.

3.2 Exclusion Criteria:

- Participant does not qualify for an allogeneic transplant due to medical screening, underlying disease, or lack of alternative donors.
- Any condition that compromises compliance with the procedures of this protocol, as judged by the principal investigator.

3.3 Informed Consent Process

All participants will be provided a consent form describing the experimental nature of the study with sufficient information for participants to make an informed decision regarding their participation.

The attending physician discusses the rationale, logistics, risks, and benefits of the study with the patient. Alternative therapies are discussed. The subject's bill of rights is reviewed. The recipient is given a copy of the consent form to take home and read. Then a meeting is scheduled for a consent conference to review the rationale, logistics, treatment plan, risks, benefits and consent form. The subject's bill of rights is reviewed with an emphasis placed on voluntary participation. Patients are given time to ask questions and do not need to sign the consent form until they are ready to proceed. In general, there is one hour devoted to the consent discussion with a clinical nurse specialist or research nurse educator. The attending physician is available to discuss the study with the patient at any time.

For pediatric patients, all efforts will be made to have both parents sign. If one parent is unable to sign, the reason will be documented in the consent note that is part of the patient permanent electronic medical records.

During the consent teaching, the physician, clinical nurse specialist or research nurse frequently asks questions of the subject to assess their understanding and a consent note is written documenting the patients understanding. For patients that are not fluent in English, the consent procedure is performed with an interpreter present (or via telephone), or a signer for those that are hearing impaired. Consents are translated into Spanish as needed. Patients are evaluated by a physician, nurse coordinator, clinical research nurse or clinical nurse specialist and social worker. Any member of the team can request a psychiatric evaluation if a concern of competency to provide consent is raised

3.4 Study Timeline

There will be no primary completion timeline to this study since the goal isto care for all HSCT recipients that need manipulated transplant graft. Subjects will continue to be followed on study until death or per institutional guidelines, whichever is longer.

4. PATIENT CONDITIONING, TRANSPLANT, AND POST-TRANSPLANT CARE

4.1 Patient Conditioning

Patient conditioning will be determined by disease and institutional guidelines for treatment.

4.2 Supportive Care Guidelines

Standard supportive care guidelines will be followed as per institutional standards and may vary with the condition or problems of the individual patients.

4.3 Criteria for Removal from Study

Conditions for individual patient termination:

- Disease progression
- Need for exclusionary concurrent treatment (per PI discretion)
- Withdrawal of informed consent
- Protocol non-compliance

The Principal Investigator may terminate the study for any of the following reasons:

- Significant toxicities related to the product graft
- If it becomes clear that the study treatment is less effective than other available treatments.

4.4 Duration of Participation in the Study and Follow-up.

Patients will remain in the hospital until there is evidence of engraftment of donor cells as well as recovery from the side effects of transplant conditioning. When the patient has engrafted and meets institutional hospital discharge criteria, they will be discharged from the inpatient facility. Patients will be followed as outpatients at regular intervals in the Bass Center Outpatient Center in the Stem Cell Transplant Clinic. Duration of participation and follow up in study will conclude at day 100 post-transplant.

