Objectives	This is a prospective study to provide access to an investigational device and reagents used for progenitor cell sorting of a stem cell transplant donor graft to determine the ability of CD34+ cell selection and T Cell depletion (using the
Objectives	CliniMACS [®] device as the sole GvHD prophylaxis) to prevent severe (grade III-IV) acute GvHD in recipients of mismatched related or unrelated donor hematopoietic stem cell transplants or with borderline organ function who might not endure the often toxic side-effects of traditional post-HSCT immunosuppressive therapy.
Primary Endpoint(s)	The primary endpoint of the study is the incidence of severe (grade III/IV) acute GvHD occurring by Day +100 after transplant.
Secondary Endpoint(s)	Outcomes measures for the secondary endpoints will include: Engraftment: The incidence of primary graft failure and graft rejection will be determined. Chimerism at Day 100: The percentage of donor cells will be reported for all evaluable (without disease progression) patients. Immune recovery: The time to CD4 count >100 and > 200 and PHA≥ 10% and 30% will be calculated. Severe toxicities: The incidence of severe toxicities will be determined. This will include grade 3/4 stem cell product infusion-related toxicity. Post-transplant infections (bacterial, viral and fungal): Post-transplant infections will be described by incidence and type. Post-transplant lymphoproliferative disease (PTLD): The incidence of PTLD will be calculated. Transplant-related mortality (TRM): The incidence of TRM will be calculated at Day 100 after transplant and at one year. Disease-free survival. Overall survival: Overall survival will be estimated using the Kaplan-Meier method. Device (CliniMACS®) performance parameters: The parameters will be summarized for all products that are processed and median and ranges will be determined.
Study Design	Participants will be enrolled with alternative (mismatched/haplocompatible) related/unrelated donors or matched related/unrelated donors for an initial HSCT.
Study Centers	This is a Stanford University, Principle Investigator (PI) initiated protocol conducted at LPCH and Stanford Hospital and Clinics.
Duration of Study per Subject	Individual participants will be followed for outcomes related to the experimental device including acute and chronic GvHD and engraftment for a minimum of one year. Subsequent follow-up care will follow the standard for all transplant patients.

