1.0 OBJECTIVES

A major issue in alternative donor (mismatched related and unrelated donor) transplantation is the development of graft-versus-host disease (GvHD). For those who cannot receive post-transplant immunosuppressive therapy, any form of graft versus host disease, even with a matched related or unrelated donor can also be a complication. Several clinical trials have shown that the use of T cell-depleted peripheral blood stem cells (PBSC) reduces GvHD in hematopoietic stem cell transplants (HSCT). By using a purified stem cell graft, there is a reduced risk of post-transplant graft versus host disease in patients who have a mismatched donor or cannot receive post-transplant immunosuppression.

This is a prospective study to provide access to an investigational device and reagents used for progenitor cell sorting. The hypothesis is that the CliniMACS® System will allow for a manipulated graft – with augmented CD34+ cells and T cell-depleted numbers --- in a ratio that will prevent severe (grade III/IV) acute GvHD (as defined on appendix C) without the use of prophylactic post-transplant immunosuppression. The incidence of grade III/IV acute GVHD is predicted to be lesser than 10% based on similar ongoing trials (17).

The objective is to manipulate (alter the ratio) specific cells in the donor graft to determine the ability of augmented CD34+ cells and T cell-depleted products to prevent severe (grade III/IV) acute GvHD in recipients of mismatched related donor hematopoietic stem cell transplants as well as to candidates of allogeneic (allo) transplant with borderline organ function -- who might not endure the often toxic side- effects of traditional post-HSCT immunosuppressive therapy.

The patients will receive conditioning therapy based on their diagnosis and per instructional guidelines for treating the disease. The transplant recipients will be followed for one year post- transplant for the development of GvHD, engraftment, post-transplant infections, disease relapse, and overall survival.

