In a retrospective review of the experience of 3 investigators in the U.S. (Cowan, Gilman, Sleight) with alternative (haplocompatible) donor transplant using CD34+ cell selection for T cell depletion, 13/18 (72%) were surviving with follow-up of 7 months – 7 years (median 31 months)(22). The median patient age was 8 years (range 1-20). Patient with malignancy (n=13) included: AML - CR1 (primaryinduction failure, failed cord blood transplant) [1], CR2 [3]; MDS - RA/RARS [2], RAEB [2]AM (and Fanconi anemia, FA) [1]; CML - CP2 [1]; ALL - CR3 [2]; NHL - CR2 [1]. Patients with non-malignant (n=5) disease included severe aplastic anemia (1 with prior bone marrow transplant three years earlier) [4] and Wiskott-Aldrich syndrome [1].

Fourteen donors were a 3/6 HLA match and 5 were a 4/6 match (one patient had two transplants using different donors). A CD34-positive selection device – Miltenyi CliniMACS $^{\otimes}$ (15), Isolex (3) – was used to select stem cells and deplete T lymphocytes. Patients received a median of 18 x 10 6 CD34+ (stem) cells/kg (range 6-28) and 3 x 10 4 CD3+ (T) cells/kg (range 0.3-11).

Sustained primary engraftment occurred in 15/18 (83%) patients. Primary graft failure occurred in one patient. Two patients had immunological rejection following HHV-6 reactivation. They both engrafted after a second transplant; therefore the overall engraftment rate was 94%. The median time to an ANC >0.5 x 10⁹/L was 12 days (range 9-21). Platelet recovery occurred in 16/18 at a median of 17 days (range 9-22). Grade II acute GvHD was seen in 4/17 patients (24%). Grade III-IV acute GvHD was seen in 1 pt. (6%) with overlap syndrome (acute + chronic GvHD) associated with HHV-6 reactivation. Nine patients received DLI and/or stem cell boosts (boosts for graft rejection); 4 had grade II GvHD (3/4 had a history of acute GvHD) and none had grade III-IV GvHD. After DLI and/or stem cell boost, two patients developed extensive chronic GvHD and one developed overlap syndrome. The day 100 mortality and one year transplant-related mortality were 11% and 19%, respectively. Four patients (of 13 at risk, 31%) have relapsed; 1 patient with cytogenetic relapse is in CR > 1 year later. The 2 year predicted survival is 64% (60% for 13 patients with malignant disease and 75% for 5 patients with non- malignant disease).

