Infections were common. All patients were at risk for CMV reactivation. Seven patients (39%) reactivated CMV. All cases were responsive to anti-viral therapy and/or DLI. No CMV disease was seen. Seven patients had adenovirus reactivation and six had HHV-6 reactivation. EBV reactivation occurred in 5/18 (28%) patients, three of whom manifested signs of post-transplant lymphoproliferative disorder.

Patients received a median of 3×10^4 CD3+ cells/kg at the time of transplant. Some patients received additional donor T cells (DLI) for viral reactivation. At three months post-transplant, only 4 of the 15 evaluable patients had a CD4 count > 100. By nine months post-transplant, 10 of the 13 evaluable patients had a CD4 count > 200.

There is an ongoing study at the University of California, San Francisco Medical Center of a prospective trial of CD34+ selected (with the CliniMACS® device) PBSC from mismatched related donors (protocol CC# 01151). Patients received a conditioning regimen including TBI 1200 cGy, thiotepa, fludarabine, and rabbit-ATG (3.5 mg/kg). Patients received a fixed T cell dose of 3 x 10⁴/kg at the time of transplant. Seventeen evaluable patients have been reported with the following diagnoses: ALL (3), AML (6), biphenotypic leukemia (1), CML (1), MDS (1), aplastic anemia (2), congenital amegakaryocytic thrombocytopenia (1) combined immunodeficiency (1), and hemophagocytic lymphohistiocytosis (1).

Twelve of the 17 (65%) were alive and well as of 2010, with follow-up ranging from 3 months to 6.5 years (median follow-up 2.5 years). Survivors include 7/12 (58%) with malignant disease and 5/5 (100%) with non-malignant disease. One patient died at 7 months after transplant due to parainfluenza and Paecilomyces infections and

[figure not shown]
another died at 23 months after transplant due to disseminated Mucor infection, a fungus from the class of Zygomycetes. There was no severe (grade III/IV) acute GvHD. Only 3/17 (18%) of patients achieved > 100 CD4+ T cells/uL by 100 days after transplant and 3/4 of these patients either had received donor T cell infusion for serious viral infections prior to 100 days or had GvHD (in which case the T cells probably represented those causing the GvHD and not providing protection against infection).

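### Section 4.4 ends study follow-up at day 100, but the synopsis and section 1.0 give one year; if 4.4 is followed, one-year TRM cannot be estimated from study follow-up

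*Combined protocol and SAP*

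**What the plan says.** Four places give a length of follow-up.

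- **Section 4.4** (Duration of Participation in the Study and Follow-up): "Duration of participation and follow up in study will conclude at day 100 post-transplant".
- **Synopsis, Duration of Study per Subject:** participants are followed for device-related outcomes, "including acute and chronic GvHD and engraftment for a minimum of one year"; care after that follows the standard for all transplant patients.
- **Section 1.0:** "The transplant recipients will be followed for one year" after transplant, for GvHD, engraftment, infections, relapse and overall survival.
- **Section 3.4:** "Subjects will continue to be followed on study until death or per institutional guidelines, whichever is longer".

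The synopsis list of secondary endpoints includes two items that depend directly on this length. For TRM: "The incidence of TRM will be calculated at Day 100 after transplant and at one year". For immune recovery: "The time to CD4 count >100 and > 200", together with PHA thresholds. Disease-free and overall survival are also listed, the latter by Kaplan-Meier. Section 2.4 lists chronic GvHD and TRM among the assessments for all recipients. It makes the standard CIBMTR schedule and forms the follow-up schedule for this study, without giving a length. Section 11.2 says study-specific CRFs in REDCap document outcomes for analysis.

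**The concern.** Section 4.4 is where study staff would look to decide when a patient is finished. Its sentence covers both participation and follow-up, so it cannot easily be read as closing only the treatment phase while outcome collection continues. A patient closed under it leaves observation 265 days before one of the two time points at which TRM is to be reported.

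TRM is the main safety outcome apart from GvHD for a T-cell-depleted graft, and slow immune recovery with late infection is the weakness that section 2.1 itself identifies. Those outcomes need the period after day 100.

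**Working it through.** **1. Comparison of the statements.** The plan gives no figure to reproduce here; the check is of consistency and estimability.

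| Place | Length of follow-up | Long enough for one-year TRM? |
|---|---|---|
| 4.4 | ends at day 100 | no |
| Synopsis, duration | at least one year | yes |
| 1.0 | one year | yes |
| 3.4 | until death or institutional guidelines | not fixed |
| 2.4 | CIBMTR schedule | length not given |

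Only 4.4 rules out the one-year endpoint.

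**2. Estimability under 4.4.** The unobserved part of the year is 365 − 100 = 265 days, and 265/365 = 73%. If every survivor is censored at day 100, the risk set is empty from day 100 onward. A Kaplan-Meier or cumulative-incidence estimate at day 365 is then undefined. The synopsis rules out imputation of missing data, so the plan offers no fallback.

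To show what remains, assume that 3 of the 30 patients have died of transplant-related causes by day 100 and the other 27 are alive and closed. One-year TRM is then known only to lie between 3/30 = 10% and 30/30 = 100%. The 3 is an assumption for illustration.

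**3. Do transplant-related deaths occur after day 100?** For the retrospective review of 18 patients, section 2.1 reports: "The day 100 mortality and one year transplant-related mortality were 11% and 19%, respectively". The gap is 19 − 11 = 8 percentage points, or 0.08 × 18 = 1.4 patients. The 11% is labelled mortality rather than TRM, and 19% is not a whole number of 18 patients (3/18 = 17%, 4/18 = 22%), so the two figures may not share a method or denominator. They suggest that the two time points differ, but are too few to estimate a late share.

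**4. CD4 recovery by day 100.** Inputs are from section 2.1, with exact (Clopper-Pearson) 95% intervals.

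- *Prospective series:* "Only 3/17 (18%) of patients achieved > 100 CD4+ T cells/uL by 100 days after transplant". Not reached: 17 − 3 = 14, and 14/17 = 82% (57% to 96%).
- *Same series, other reading:* the sentence goes on to describe three out of four such patients. If four had reached the threshold, 17 − 4 = 13, and 13/17 = 76% (50% to 93%).
- *Retrospective series at three months:* 4 of 15 evaluable were above 100. Not above: 15 − 4 = 11, and 11/15 = 73% (45% to 92%).
- *Retrospective series by nine months:* 10 of 13 evaluable were above 200, or 77% (46% to 95%).

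On these figures most times to CD4 >100 would be incomplete at day 100, while follow-up to one year would probably capture most of them. Some of the 17 may have died before recovery, so not every one would be a censored time. The series are not pooled, because they may share patients. They are not scaled to this trial, because they are mismatched-donor series and this trial also admits matched donors with any conditioning regimen.

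**5. Primary endpoint.** Grade III/IV acute GvHD is counted by day +100, so it is observed in full under every version.

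**The case against.** The best defence is that the data will exist anyway. Section 2.4 makes the CIBMTR schedule this study's own follow-up schedule, and the synopsis provides for continuing care after one year. This has weight: a reader might infer from 4.4 that one-year outcomes will certainly be lost, and the documents do not support that. But no length is given for the CIBMTR schedule, its forms are not shown to carry the CD4 data, and nothing says the study uses them once participation has ended under 4.4. It lessens the likely loss without removing the contradiction.

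A second defence is that day 100 may be the intended end. The primary endpoint, chimerism and expedited death reporting all use it, and the documents do not say which statement is current. That also stands in part. It is nevertheless hard to hold alongside a stated one-year TRM endpoint and two explicit one-year statements.

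A reader might also infer that the other three durations agree with one another. They do not fully: section 3.4 has no fixed end, and asking for the longer of death and institutional guidelines is unclear.

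Two further extensions are tempting and fail. One is that patients removed under section 4.3 would go ungraded for GvHD; section 1.0 names GvHD first among the outcomes followed for a year, so no such special gap is shown. The other is to project losses from the 19% two-year chronic GvHD rate in the earlier AML trial or from the one infection death dated at 7 months in the prospective series. The first has no day-100 comparator; the second is a single event in a series where three of the five deaths are undated.

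**Conclusion.** The contradiction is real and should be fixed. Conditional on 4.4 being followed, one-year TRM is not estimable from study follow-up, and overall survival, disease-free survival, chronic GvHD and CD4 recovery are observed only for the first 100 days. That consequence follows from the wording and needs no outside assumption.

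The size of the loss for CD4 recovery (roughly three-quarters or more not yet above 100 by about day 100) is indicative only. It rests on 17 and 15 mismatched-donor patients with wide intervals. No share of late TRM is estimated.

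The primary endpoint is safe. That one year is the intended length is an inference from the TRM endpoint, the synopsis and section 1.0; what the documents establish is that the statements must be reconciled.

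**What to change.** 1. In section 4.4, replace the day-100 conclusion with study outcome follow-up of at least one year, matching the synopsis and section 1.0. This is the shortest length that supports the one-year TRM endpoint.
2. In section 3.4, say whether follow-up beyond one year is on study or standard care, so that the protocol gives one end of participation.
3. Name the data source after day 100 (CIBMTR forms, the study REDCap CRFs, or both) and confirm that it captures TRM with cause of death, chronic GvHD, relapse, vital status and CD4 counts with dates.

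The cost is amendment wording with IRB approval under section 11.1, and some outcome data entry to one year for 30 patients. If the chosen forms do not already hold CD4 counts, a CRF field is also needed. The consent pages were not available for this review, so the duration stated there should be checked against the amended text.
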